1 SYNOPSIS

Title: A Prospective, Multi-center, Open-label Study to Evaluate Subject Satisfaction and Natural Outcomes Following Administration of BOTOX® Cosmetic (Botulinum Toxin Type A) Purified Neurotoxin Complex in Subjects with Upper Facial Lines (Glabellar Lines, Lateral Canthal Lines, and Forehead Lines)

| | |
|--|---|
| Background and Rationale: | BOTOX Cosmetic is an acetylcholine release inhibitor and a neuromuscular blocking agent approved for aesthetic treatment of glabellar lines (GL), lateral canthal lines (LCL), and forehead lines (FHL). It is typical for some clinicians to administer lower than labeled doses of botulinum toxin to avoid a "frozen" look. The intent of this study is to evaluate subject satisfaction and natural outcomes following administration of 64 Units (U) of BOTOX Cosmetic for multiple upper facial areas (GL, LCL, and FHL). |
| Objective and Primary Endpoint: | The objective of this study is to evaluate subject satisfaction and natural outcomes following simultaneous treatment of multiple upper facial lines (GL, LCL, and FHL) with 64 U of BOTOX Cosmetic. The primary endpoint is the responder status of Mostly satisfied or Very satisfied on the Facial Line Satisfaction Questionnaire (FLSQ) Follow-up Item 4 at Day 30. |
| Investigators: | Multi-center |
| Study Sites: | Approximately 10 sites |
| Study Population and Number of Subjects to be Enrolled: | Approximately 100 subjects in general good health with moderate to severe GL, LCL, and FHL. |
| Investigational Plan: | This is a prospective, multicenter, open-label study. Eligible subjects will receive a single fixed dose of 64 U of BOTOX Cosmetic on Day 1. Subjects will be followed monthly for up to 180 days after treatment. |
| Key Eligibility Criteria: | Adult male or female; ≥ 18 years of age; moderate to severe GL, LCL, and FHL, as determined by the investigator at maximum contraction at Day 1 |
| Study Drug and Duration of Treatment: | Single treatment of BOTOX Cosmetic (64 U) |
| Date of Protocol Synopsis: | 14 December 2023 |

2 INTRODUCTION

2.1 Background and Rationale

Why Is This Study Being Conducted?

BOTOX Cosmetic (onabotulinumtoxinA/Botulinum Toxin Type A) is an acetylcholine release inhibitor and a neuromuscular blocking agent indicated in adults for the temporary improvement in the appearance of moderate to severe glabellar lines (GL) associated with corrugator and/or procerus muscle activity, moderate to severe lateral canthal lines (LCL) associated with orbicularis oculi activity, and moderate to severe forehead lines (FHL) associated with frontalis muscle activity.^{1,2}

The contraction of these facial muscles serves a role in communicating an emotional state, which influences both how an individual presents themselves as well as how they are perceived by others.³ Over time, the repetitive contraction of facial muscles, along with degenerative changes due to aging, can negatively affect social interactions, social perceptions and, ultimately, self-esteem.⁴

Facial rejuvenation has been rapidly gaining ground to improve subject satisfaction with facial appearances, which is often described as achieving a "natural and relaxed" look. It is typical for some clinicians to start with less than labeled doses of botulinum toxin to avoid a "frozen" look. As more experience has been gained, botulinum toxin dosing, precise placement, and injection techniques have become more fine-tuned. As a result of these advances, healthcare professionals have learned that proper botulinum toxin procedures can yield a natural look that drives subject satisfaction.⁵

Although limited, several studies have focused on patient outcomes associated with the improvement in signs of aging. The HARMONY study investigated the impact of fillers and onabotulinumtoxinA in a pan-facial approach and demonstrated that minimally invasive, multimodal treatment resulted in improvements in FACE-Q scores and perceived age, indicating a high degree of patient satisfaction and a younger facial appearance.⁶ In addition, when independent observers were provided with enrolled subjects' paired before and after treatment images, the independent observers reported that subjects appeared to have a higher social status, look nearly 5 years younger, more healthy, approachable, more attractive, and more successful at attracting others after treatment.⁷

Significant improvements in patient-reported outcomes (PROs) have also been reported in a Phase 3 study assessing the effectiveness of onabotulinumtoxinA treatment of GL, LCL, and FHL.⁸ Subjects were highly satisfied with onabotulinumtoxinA treatment and reported significant improvement in emotional and psychological well-being compared to placebo. Subject satisfaction remained high throughout the 6-month double-blind period, and improvements were maintained with repeated onabotulinumtoxinA treatment during the following 6-month open-label period.

The purpose of this study is to evaluate subject satisfaction and natural outcomes following BOTOX Cosmetic treatment of upper facial areas (GL, LCL, and FHL).

2.2 Benefits and Risks to Subjects

The clinical efficacy and safety profile of BOTOX Cosmetic has been demonstrated in multiple clinical trials across several indications, with favorable benefit risk profiles. In general, adverse reactions occur within the first few days to weeks following injection of BOTOX Cosmetic and, while generally transient, may have a duration of several months or, in rare cases, longer.

While Allergan (an AbbVie company) does not consider Coronavirus disease 2019 (COVID-19) to be a safety concern for BOTOX Cosmetic due to its mechanism of action and route of administration, the sponsor is monitoring COVID-19 events during the pandemic closely. A review of COVID-19 events for the period of 01 January 2019 through 31 December 2021 did not identify any new or significant safety findings for the subjects receiving BOTOX Cosmetic treatment. Overall, the clinical course and presentation of patients with COVID-19 infection coincident with BOTOX Cosmetic is consistent with what has been described for the general population. Considering the COVID-19 pandemic and based on the limited information to date, no additional risk to study participants is anticipated with the use of BOTOX Cosmetic.

For further details, please see findings from completed studies, including safety data in the current BOTOX Cosmetic investigator's brochure.

3 OBJECTIVES AND ENDPOINTS

3.1 Objectives, Hypotheses, and Estimands

Objective

The objective of this study is to evaluate subject satisfaction and natural outcomes following the administration of 64 U of BOTOX Cosmetic in subjects with upper facial lines (GL, LCL, and FHL).

Clinical Hypothesis

Single treatment of upper facial lines with BOTOX Cosmetic at 64 U can lead to subject satisfaction and natural outcomes.

Estimands

The estimand corresponding to the primary endpoint is as follows:

- The proportion of subjects receiving treatment of BOTOX Cosmetic 64U who achieve the responder status of *Mostly satisfied* or *Very satisfied* on the Facial Line Satisfaction Questionnaire (FLSQ) Item 4 at the Day 30 assessment in the modified intention-to-treat (mITT) population. Subjects who have any intercurrent event resulting in not having a Day 30 assessment will not be included.

The estimand corresponding to the secondary endpoint is as follows:

- The mean change from baseline in subject assessment based on Rasch-transformed score of FACE-Q Psychological Function at the Day 30 assessment for subjects who receive BOTOX Cosmetic 64 U in the MITT population. Subjects who have any intercurrent event resulting in not having a Day 30 assessment will not be included.

3.2 Primary Endpoint

[figure not shown]
The primary endpoint is the responder status of *Mostly satisfied* or *Very satisfied* on the Facial Line Satisfaction Questionnaire (FLSQ) Follow-up Item 4 at Day 30.

[figure not shown]
3.3 Secondary Endpoint

Secondary endpoint is

- Change from baseline in subject's assessment based on Rasch-transformed score of FACE-Q Psychological Function scale at Day 30

3.4 Additional Endpoints

3.5 Safety Endpoints

The safety endpoint is the incidence of adverse events (AEs).

4 INVESTIGATIONAL PLAN

4.1 Overall Study Design and Plan

This is a 6-month, prospective, multicenter, open-label study to evaluate subject satisfaction and natural outcomes following the administration of BOTOX Cosmetic 64 U for the treatment of upper facial lines.

The study will enroll approximately 100 subjects with moderate to severe GL, LCL, and FHL as assessed by the investigator. Out of the approximately 100 enrolled subjects:

- approximately 20% of the study population will be treatment naïve to any botulinum toxin of any serotype for any indication,
- approximately 20% of the study population will be self-identified as male,

- approximately 20% of the study population will be self-identified as Asian, and
- approximately 20% of the study population will have Fitzpatrick skin phototypes of IV, V, or VI.

A review of individual site data will be conducted once a sufficient number of subjects has been enrolled. The site will be permitted to enroll additional subjects upon sponsor approval. This process may be repeated as needed.

On Day 1, after subjects are verified to meet all eligibility criteria and have completed all baseline study procedures, they will receive 64 U of BOTOX Cosmetic. Each subject will receive a total of 16 injections (0.1 mL or 4 U of BOTOX Cosmetic per injection), with 5 injections in the glabellar complex, 3 injections in each of the lateral canthal area (6 total injections), and 5 injections in the frontalis muscle.

There are seven in-clinic visits: screening/baseline/treatment (Day 1), post-treatment follow-up visits (Days 30, 60, 90, 120, 150), and study exit (Day 180 or Early Exit). The study schema of the study is shown in [Figure 1](#).

Further details on study procedures are located in the Operations Manual ([Appendix E](#)).

Figure 1. Study Schema

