4.2 Discussion of Study Design

Choice of Control Group

This is an open-label study. There is no separate control group.

Appropriateness of Measurements

The primary efficacy measure used in this study (FLSQ) is a validated measure. Allergan has also developed and validated upper facial line severity scales (AGLSS, LCLSS, and FHLSS) in accordance with the United States Food and Drug Administration requirement. All efficacy-related measurements in this study are standard for assessing facial aesthetics correction (for GL, LCL, and FHL). All clinical procedures in this study are standard and generally accepted.

Suitability of Subject Population

The study population will include male and female adults with moderate to severe GL, LCL, and FHL at maximum contraction as assessed by investigators using the AGLSS, LCLSS, and FHLSS, respectively. To avoid confounding the study results, washout from prior facial aesthetic treatments is required as described in the eligibility criteria.

Selection of Doses in the Study

BOTOX Cosmetic is currently approved for aesthetic treatment of GL, LCL and FHL. The total dose, dilution, injection pattern, and route of administration will follow the approved label, and each eligible subject will receive a fixed dose of 64 U of BOTOX Cosmetic on Day 1 (20 U to the glabellar complex, 24 U to the lateral canthal areas, and 20 U to the frontalis muscles).

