7.6 Interim Analysis

Not applicable for this study.

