2.3 Treatment Assignment and Blinding

This is an open-label study. Hence, there is no subject randomization or blinding for the study treatment assignment.

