12.0 Interim Analyses

No interim analysis is planned for this study.

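### Does the unscoped site data review in Protocol 4.1 let satisfied sites be over-sampled and the pooled responder rate drift upward?

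*Protocol*

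**What the plan says.** Protocol 4.1 (Overall Study Design and Plan) sets a total of about 100 subjects and lists four targets of roughly 20% each: toxin-naïve, male, Asian, and Fitzpatrick IV to VI. It continues: "A review of individual site data will be conducted once a sufficient number of subjects has been enrolled". Then: "The site will be permitted to enroll additional subjects upon sponsor approval. This process may be repeated as needed". The section does not define the number that triggers the review, the data reviewed, the criteria for approval or a limit per site. The synopsis gives about 10 sites. SAP 2.2 repeats the design but not the review.

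The study has no comparator (Protocol 4.2: "There is no separate control group") and is unblinded (SAP 2.3: "Hence, there is no subject randomization or blinding for the study treatment assignment"). On looks at the data before the end, Protocol 7.6 says "Not applicable for this study" and SAP 12.0 says "No interim analysis is planned for this study". The primary result is the proportion of mITT subjects who are mostly or very satisfied on FLSQ Item 4 at Day 30. It is summarised without a test and with a Clopper-Pearson interval (SAP 9.1, 9.3.2).

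**The concern.** In a randomised trial, a shift in the mix of sites affects both arms and largely cancels. Here there is one arm and one proportion, so any shift goes straight into the estimate. Satisfaction may depend on injector technique and on which subjects a site recruits. If the sponsor saw Day 30 answers and let the best-looking sites grow, the later subjects would come disproportionately from sites with high true rates, and the pooled figure would overstate the average site. Nothing in the documents supplied excludes FLSQ or FACE-Q results from the review. The visible SAP text has no by-site summary, and SAP 9.3.3 plans no sensitivity analysis, so a reader of the results could not see whether this had happened. The statements that there is no interim analysis might also seem to conflict with a repeated review of site data.

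**Working it through.** **1. The plan's own precision figure.** Inputs from Protocol 7.8: 75% expected, n = 100, 95% interval, correction of −1/2. With x = 75:

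- centre = ln[(75 − 0.5)/(25 − 0.5)] = ln(74.5/24.5) = 1.112
- SE = √(1/75 + 1/25) = 0.231
- limits on the logit scale = 1.112 ± 1.96 × 0.231 = 0.659 and 1.565
- back-transformed = 65.9% and 82.7%, that is −9.1 and +7.7, width 16.8 points

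This matches the plan. Half the width is 8.4 points. The Clopper-Pearson interval for 75/100 is 65.3% to 83.1%, half-width 8.9.

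**2. What outcome-driven approval would do.** The documents give no between-site variation, so the intra-site correlation (ICC, ρ) is assumed. Model: 10 sites, with site rates from a Beta distribution with mean 0.75 and SD = √(ρ × 0.75 × 0.25), which is 0.061, 0.097 and 0.137 for ρ = 0.02, 0.05 and 0.10. Each site enrols a first batch. The places left out of 100 then go to the sites with the most observed responders. First-batch subjects are unbiased for 75%, so

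bias = f × (mean true rate of the chosen sites − 75%),

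where f is the share of all subjects enrolled after the review. Example: 5 per site, then 50 places to the best 5 sites, gives f = 0.5. At ρ = 0.10 the chosen sites average 80.9%, so the bias is 0.5 × 5.9 = about +3.0 points.

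Bias in percentage points, by simulation:

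| Rule | ρ = 0.02 | ρ = 0.05 | ρ = 0.10 |
|---|---|---|---|
| 5 per site, then 50 to best 2 | +1.0 | +2.3 | +4.2 |
| 5 per site, then 50 to best 5 | +0.7 | +1.6 | +3.0 |
| 8 per site, then 20 to best 2 | +0.5 | +1.2 | +2.0 |
| 5 per site, 2 of 5 Day 30 results in, then 50 to best 5 | +0.4 | +1.0 | +2.0 |
| 5 per site, then 50 to all but the worst 2 | +0.4 | +0.8 | +1.5 |
| 8 per site, then 20 to best 5 | +0.3 | +0.8 | +1.4 |
| 8 per site, 3 of 8 Day 30 results in, then 20 to best 5 | +0.2 | +0.5 | +1.0 |

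At ρ = 0 the bias is nil under each rule tried. If ρ were as high as 0.20, the first two rules would give about +6.7 and +5.2. When the extra places go to sites chosen without regard to outcome, the mean pooled rate is 74.9% to 75.1% in all scenarios run.

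**3. Interval coverage.** With 5 per site and 50 places to 5 sites, Clopper-Pearson coverage is 89.8% when sites are picked on outcome and 90.2% when picked at random (ρ = 0.05), or 81.2% against 84.2% (ρ = 0.10). Most of the shortfall from 95% comes from clustering by site, which is a different matter and would be the same with an outcome-free review.

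**4. The text itself.** The review is triggered by the number enrolled, not by the number who have reached Day 30. It stands directly after the four enrolment targets. Protocol Appendix E gives its purpose as more flexible enrolment and review of site data. Checking a site's conduct and subject mix is not an efficacy analysis, so there is no conflict with Protocol 7.6 or SAP 12.0. Those two sections point away from looks at outcomes.

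**The case for a change.** The strongest reply is that the plan should not leave this to good sense. "This process may be repeated as needed" means later reviews could take place when many Day 30 answers are in hand. The approver is the sponsor, there is no data monitoring committee, and one sentence limiting the review to non-outcome data would cost almost nothing. A shift of 3 to 4 points would be a substantial part of the 8.4-point half-width.

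Part of this stands. The scope, trigger and approval criteria are indeed unwritten, and the Operations Manual, to which Protocol 4.1 refers for procedures, is not available to settle the matter. But the case reads silence as permission. It also needs three things at once: outcome data in the approvers' hands, ranking of sites by those data, and large differences between sites. The larger figures further require that half the study go to the top-ranked sites. The possible additions bring little. A table by site would describe the result without changing it. A cap per site could hinder the 20% targets if only a few sites can supply those subjects.

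**Conclusion.** No change is needed. This is a gap in detail that a sponsor fills sensibly by using the review for enrolment targets, data quality and site conduct. On that reading the pooled rate is unbiased, and the planned 16.8-point width is unaffected because the total and the expected rate stay the same. If approvals did follow Day 30 satisfaction, the upward bias would be about +0.2 to +2 points under moderate rules and up to about +4 points under the harshest one, for an assumed ICC of 0.02 to 0.10. Neither the rule nor the ICC comes from the documents. The 75% used as the true value is an equal-weight average over sites; the estimand in Protocol 3.1 counts subjects and sets no site weights. There is no hypothesis test, success threshold or comparator, so no decision in the plan turns on a shift of this size.

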7.8 Sample Size Determination

No formal sample size calculation was performed.

For a conservative expected proportion of 75% for the primary endpoint (proportion of subjects reporting *Mostly satisfied* or *Very satisfied* on the FLSQ Follow-up Item 4 at Day 30), a sample size of 100 subjects in the study is required for an adjusted logit-based 95% binomial confidence interval to have a width of 16.8% (interval is 75% – 9.1% to 75% + 7.7% with recommended correction of – 1/2).⁹

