5.0 Subject Disposition

The total number of subjects who were screened, enrolled and treated will be summarized.

A summary of subject accountability will be provided where the number of subjects in each of the following categories will be summarized:

- Number of subjects screened
- Number of subjects treated
- Number of subjects completed the study
- Number of subjects discontinued from the study
 - Reasons for discontinuation from the study

The number of subjects in each analysis population will also be summarized.

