9.0 Efficacy Analyses

9.1 General Considerations

The following considerations apply to all efficacy analyses, unless otherwise specified:

- All efficacy analyses will be conducted in the mITT population unless otherwise specified.
- Day 1 is defined as the day on which the study treatment is first received.

- Baseline for effectiveness parameters will be the last non-missing assessment prior to or on Day 1.
- Study day is always relative to Day 1.
- Change from baseline will be computed as postbaseline minus baseline.
- Continuous variables will be summarized descriptively using number of subjects with observed values (n), mean, standard deviation (SD), median, minimum (min), and maximum (max). In addition, 95% confidence intervals (CIs) will be performed using paired t-tests for change from baseline endpoints.
- Categorical variables will be summarized descriptively using number of subjects with observed values or events (n) and the percentage of subjects with observed values or events.
- Analyses based on responder rates will include a 95% CI for the responder rate using the exact binomial distribution (Clopper-Pearson approach).
- All CIs will be 2-sided 95% CIs, unless stated otherwise.

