9.3.3 Sensitivity and Supplementary Analyses of the Primary Efficacy Endpoint(s)

Not applicable.

[figure not shown]

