9.5 Additional Efficacy Analyses

9.6 Efficacy Subgroup Analyses

For the primary and secondary endpoints, analyses will be conducted using the following subgroups with descriptive summary statistics provided:

- Toxin Naïve (Yes or No)
- Sex (Female, Male)
- Race (Asian, Non-Asian)
- Fitzpatrick skin type (Type I-III, Type IV-VI)

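### Does uncapped, sponsor-approved growth of sites make the pooled exact confidence interval for the primary endpoint misleading?

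*Protocol*

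**What the plan says.** Protocol 4.1 follows the four 20% enrolment targets with a site-level step: "A review of individual site data will be conducted once a sufficient number of subjects has been enrolled". It then adds: "The site will be permitted to enroll additional subjects upon sponsor approval. This process may be repeated as needed". The trigger number, the data reviewed, the approval criteria and any per-site limit are not given in the visible text. The Operations Manual, where they might be, is not supplied. SAP 2.2 repeats the design description without this step.

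On analysis, SAP 5.0 gives overall counts: "The total number of subjects who were screened, enrolled and treated will be summarized". SAP 9.1 attaches a two-sided 95% Clopper-Pearson interval to each responder rate. SAP 9.3.3 marks sensitivity and supplementary analyses of the primary endpoint as not applicable. SAP 9.6 reads "For the primary and secondary endpoints, analyses will be conducted using the following subgroups with descriptive summary statistics provided", and the list is toxin-naïve status, sex, race and Fitzpatrick type, not site. SAP 9.3.2 and 13.0 say that no test will be done.

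Two further places matter. The primary estimand in Protocol 3.1 is the proportion of treated mITT subjects who respond at Day 30, with no reference to sites. The SAP version history (14.0), in its entry on Section 9.5, says that listings are kept for the primary and secondary endpoints. Section 9.5 itself is blank in the public copy.

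**The concern.** The primary result is one single-arm rate with an interval, and the sample size is justified only by the width of such an interval. A Clopper-Pearson interval assumes independent subjects with a common response probability. Here subjects are treated by different injectors at about ten sites, open-label, and report their own satisfaction. Protocol 2.1 says in its background that "proper botulinum toxin procedures can yield a natural look that drives subject satisfaction", so site differences are conceivable. Protocol 4.1 lets some sites grow without a stated limit, and the more enrolment concentrates, the more any site effect weighs on the pooled rate. If the interval understated the uncertainty, the stated precision would be too optimistic, and no planned summary table would show how much each site contributed.

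**Working it through.** **Inputs from the documents.** Expected rate 75% and N = 100 (Protocol 7.8); about 10 sites (Protocol synopsis); two-sided 95% Clopper-Pearson interval (SAP 9.1). **Assumed, because the documents give neither:** the ICC and the split of subjects over sites.

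**1. The plan's own figure.** Protocol 7.8 wants the "adjusted logit-based 95% binomial confidence interval to have a width of 16.8" percentage points. With 75 responders of 100 and the −1/2 correction in the centre only:
- centre = ln(74.5/24.5) = 1.1121
- SE = √(1/75 + 1/25) = 0.2309
- limits on the logit scale = 1.1121 ± 1.96 × 0.2309
- back-transformed: 65.9% to 82.7%, that is 75% − 9.1 to 75% + 7.7, width 16.8 points.

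The figure reproduces and assumes 100 independent subjects. The Clopper-Pearson interval at 75/100 is 65.3% to 83.1%, width 17.8 points.

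**2. Target A: a wider population of sites.** Design effect = 1 + (m − 1) × ICC, with m = Σnᵢ²/N; effective N = 100/design effect. For ten sites of 10, m = 10. For five of 15 and five of 5, m = (5×225 + 5×25)/100 = 12.5. For two of 30 and eight of 5, m = (2×900 + 8×25)/100 = 20. At ICC 0.05 the design effects are 1.45, 1.58 and 1.95, and the effective N is 69, 63 and 51.

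Simulated coverage of the planned interval for a population rate of 75% (beta-distributed site rates, at least 40,000 trials per setting, site growth unrelated to outcome):

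| Split | ICC 0 | 0.02 | 0.05 | 0.10 |
|---|---|---|---|---|
| 10 × 10 | 96.3% | 94.5% | 91.5% | 86.7% |
| 5 × 15, 5 × 5 | 96.2% | 93.9% | 90.2% | 84.2% |
| 2 × 30, 8 × 5 | 96.2% | 92.3% | 86.2% | 77.3% |

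**3. Target B: the size-weighted rate at the participating sites.** With site rates pᵢ fixed, the variance of the pooled count is Σnᵢpᵢ(1 − pᵢ) = N[p̄(1 − p̄) − V], where V is the size-weighted variance of the pᵢ. Site differences therefore reduce the variance below binomial. On average pᵢ(1 − pᵢ) is 0.1875 × (1 − ICC), for example 0.1875 × 0.95 = 0.178 at ICC 0.05. Simulated coverage is about 96.3%, 96.5% and 97.0% at ICC 0.02, 0.05 and 0.10, within 0.2 points across the three splits. Unequal growth does no harm here.

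**4. What the ICCs mean.** The SD of true site rates is √(ICC × 0.1875): 6.1, 9.7 and 13.7 points at ICC 0.02, 0.05 and 0.10. At ICC 0.05 the 5th to 95th percentile of site rates runs from about 58% to 89%; at 0.10, from about 50% to 94%. Those are large differences for one fixed dose given as 16 injections in a set pattern (Protocol 4.1 and 4.2).

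**5. What an addition would buy.** A site-clustered (Korn-Graubard) interval averages 20.6 points wide against 17.7 when sites do not differ, with coverage of about 98%. For target A with two sites holding 60 subjects, its coverage is 95.5%, 93.6% and 91.7% at ICC 0.02, 0.05 and 0.10. A by-site table is free, but with 10 subjects per site chance alone gives an SD of √(0.75 × 0.25/10) = 13.7 points, as large as the true site SD at ICC 0.10.

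**The case for a change.** The best case for acting is that this is a precision-based study. The interval is its only statement of uncertainty about the primary result, so calling the study descriptive does not make the interval's validity irrelevant. Readers will want to apply the rate beyond these ten sites, and for that use the coverage loss in step 2 is real even when approval ignores outcome. Acting would also cost little: one table, one supportive interval and one sentence on the review's scope.

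Part of this stands. Anyone who generalises to other clinics should know that the interval leaves out between-site variation. The rest is weaker:
- The documents do not say that the sites are a random sample of anything, and the estimand is defined on treated subjects.
- The sentence in Protocol 2.1 is general background about technique. It is not evidence that injectors following one fixed pattern differ.
- Nothing says that satisfaction results inform approval. The step directly follows the enrolment targets, so a check of targets or data quality is at least as natural a reading. Approval that ignores outcome leaves the mean rate unbiased.
- A listing of the primary endpoint is planned. Whether it shows site is not stated, so it cannot be claimed that site contributions would stay hidden.
- The clustered interval does improve coverage when enrolment is concentrated (91.7% against 77.3% at ICC 0.10). It still falls short there, and it is needlessly wide when sites are alike. With about ten clusters, this is a trade-off and not a correction.

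**Conclusion.** No change follows. The planned interval is valid, and slightly conservative, for the rate at the participating sites, with coverage of about 96% to 97% under every setting tried. It would be too narrow only for a wider population of sites whose true rates differ: about 92% with equal sites and about 86% if two sites hold 60 subjects, at an assumed ICC of 0.05. At ICC 0.02 with equal sites it is 94.5%, practically nominal. These figures rest on assumed ICCs and site splits, a true rate of 75% and beta-distributed site rates.

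The unstated scope of the site review is missing detail, which the unseen Operations Manual may supply; the visible text does not tie approval to outcome. The absence of a by-site table is a reporting gap that a study team can fill without amending the SAP, by showing subjects enrolled, subjects with Day 30 data and responders per site, and by noting that the interval does not account for between-site variation. Neither step would alter the primary estimate or its planned interval, and with no test there is no decision to affect.
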